COMIRB Protocol

COLORADO MULTIPLE INSTITUTIONAL REVIEW BOARD
[name] [contact] [contact]

Protocol Version 3, 07/09/2015

Project Title: Aspiration in Acute Respiratory Failure Survivors

Principle Investigator: [name] MD

I. Hypothesis and Specific Aims

We hypothesize that the BSE assessment of swallowing certain consistencies will provide the most accurate diagnosis of aspiration.

A. Specific Aim #1: To develop a BSE-based non-invasive clinical prediction rule (CPR) that will accurately and efficiently diagnose aspiration in ARF survivors.

B. Specific Aim #2: To identify abnormalities in laryngeal structure and swallowing physiology that are associated with aspiration in ARF survivors.

Study Design: Prospective cohort study of patients with acute respiratory failure who require mechanical ventilation for more than 48 hours.

Inclusion Criteria:

1. Admission to an ICU.
2. Mechanical ventilation with an endotracheal tube for greater than 48 hours.

Exclusion Criteria:

1. Age < 18 years
2. Contraindication to enteral nutrition administration.
3. Pre-existing or acute primary central or peripheral neuromuscular disorder
4. Pre-existing history of dysphagia or aspiration.
5. Pre-existing head and neck cancer or surgery.
6. Presence of a tracheostomy.
7. Coagulopathy resulting in uncontrolled nasal or pharyngeal bleeding.
8. Unable to participate due to altered mental status
9. Extubated for greater than 72 hours.
10. Inability to obtain informed consent from patient or an appropriate surrogate.
11. Pregnancy
12. Imprisoned at the time of admission, anytime during the hospitalization, or anytime during the follow up period

First, a SLP will perform a comprehensive BSE on each ARF survivor.

Subsequently a second blinded SLP/investigator will perform the FEES to determine whether aspiration is truly present. The FEES examination will also identify abnormalities associated with aspiration.

For Aim #1: Primary Outcome Variable: Aspiration (PAS score of ≥ 6) on the FEES with any of the five feedings. A PAS score of ≥ 6 includes patients with both silent and non-silent aspiration.

Statistical analysis: Recursive partitioning or Classification and Regress Tree (CART) analysis creates a tree that asks a series of yes/no questions, taking the user down different branches depending on the answers. At the end of each branch will be an estimated probability of outcome.

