For Aim #2: Primary outcome variables: Presence of abnormalities in the four laryngeal functions and two swallowing physiology measures.

Statistical analysis: For each outcome and independent variable, a univariate logistic regression model will be developed.

Overall Sample Size Determination: In a simulated data analysis, a sample size of 200 yielded an area under the curve (AUC) of .75 for the resultant tree algorithm. To be conservative, we will enroll a total of 225 patients.

Significance: For the 455,000 acute respiratory failure (ARF) survivors each year, aspiration is a devastating complication that can develop after the initiation of oral nutrition.^{1,2} Occurring in as many as 44% of ARF survivors, aspiration is associated with many deleterious consequences including pneumonia, percutaneous feeding tube placement, long term care facility admission, and increased hospital

mortality.³⁻⁶ The complications of aspiration must be weighed against the consequences of inappropriately delaying the resumption of oral feeding. Delayed resumption of oral nutrition is associated with prolonged enteral tube feeding, increased caregiver burden, patient dissatisfaction, and increased health-related costs.⁷⁻¹⁰ Improving the ability to easily and accurately diagnose aspiration in ARF survivors would both reduce the frequency and severity of aspiration and limit the problems associated with delaying oral nutrition. *This proposal will develop an effective non-invasive bedside diagnostic clinical prediction rule (CPR) to detect aspiration in ARF survivors.*

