3. Our nationwide survey of SLPs identified current practices to detect aspiration in ARF survivors.¹¹ We designed, validated, and distributed a survey to 1,966 SLPs working in an inpatient setting. Each survey included questions concerning SLP staffing and availability, and methods used in the diagnosis and treatment of dysphagia and aspiration. A total of 836 SLPs completed their survey (43%), 801 of whom were actively practicing. This survey represents the largest published study to date of SLP practices for ARF survivors.

4. There is currently no uniformly used diagnostic CPR to detect aspiration in ARF survivors.¹¹ Only 29% of hospitals have formal guidelines for when critical care providers should consult SLPs in the evaluation of ARF survivors. Most SLPs performed the BSE on average 24 hours after extubation. Importantly, the majority of SLPs (60%) only use the BSE to identify aspiration in ARF survivors. Gold standard tests (VFSS and FES) are not commonly used, and there is significant geographic variability in their use (Figure 4). VFSS and FEES are also more available and more utilized at university hospitals when compared to community hospitals (p < 0.01).

5. We already have enrolled 26 ARF survivors in Aim #1 without any adverse events. A total of 50% of ARF survivors had evidence of aspiration on FEES evaluation. The diagnostic accuracy of each individual assessment of

swallowing foods and liquids of different consistencies appears to be poor for detecting true aspiration (see Table 1). *These data demonstrate feasibility to complete the studies in Aim #1.* By combining specific components of the BSE, we anticipate that we will be able to develop a more accurate diagnostic CPR for aspiration.

6. In ARF survivors, abnormalities of laryngeal function and swallowing physiology are associated with aspiration (Aim #2 data). At Boston University Medical Center, 59 ARF survivors who required mechanical ventilation for at least 48 hours underwent FEES examination including laryngeal structure and swallowing physiology assessment. Upper airway abnormalities were common including: laryngeal edema, vocal cord immobility, and vocal cord granuloma formation. Vocal cord granulomas were associated with severe dysphagia or aspiration ($p = 0.04$). This work has been submitted for publication and demonstrates the feasibility to complete the studies in Aim #2.

OBJECTIVES

Table 1: BSE accuracy for aspiration with different consistencies

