Boluses will be administered from lowest to highest aspiration risk: 1) $\frac{1}{2}$ tsp, then 1 tsp ice chips , 2) 1 tsp of nectar thick liquids, then 3 tsp of nectar thick liquids, 3) a 2 ounce patient controlled administration of nectar thick liquids, 4) 1 tsp of pureed solids (applesauce), then 10 mls of pureed solids (applesauce), 5) 5 mls of thin liquids (water or milk),15 mls of thin liquids (water or milk), and a 2 ounce patient controlled administration of thin liquids and 6) $\frac{1}{4}$ of a graham cracker.¹⁰⁷ The patient will be instructed to chew the graham cracker before swallowing. In order to limit the complexity and duration of our consistency testing, honey-thick liquids will be excluded from the protocol.

The SLP will wait for 10 seconds following the completion of each individual trial before recording the results for that consistency. The following adverse outcomes (coughing/choking, change in breath sounds, and change in voice quality, throat clearing, or change in pulse oximetry recording by > 10%) will be recorded after each trial.

If the clinician feels it is unsafe to continue with the next bolus consistency, the protocol can be stopped at any time.

Coughing/choking: Dichotomized as a single cough or choking sound within 10 seconds after diet administration (yes/no).

Change in breath sounds: Breath sounds will be assessed before and 10 seconds after the examination by either auscultating over the larynx at the thyro-cricoid space during quiet breathing or listening to the patient's breathing without a stethoscope. The SLP will record whether they used a stethoscope or not to listen for change in breath sounds. Patients will be classified as "gurgling" or "non-gurgling." Gurgling is a low/medium-pitched rattling sound on inhalation or exhalation.¹⁰⁸

Change in vocal quality: Baseline vocal quality will be assessed initially and dichotomized as normal/abnormal. Any transition from normal to abnormal vocal quality during feeding will be recorded.

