include the next branches on the trees. By splitting the data up into ten sets and choosing one set each time, ten-fold cross-validation will estimate the misclassification rate for the tree. The chosen set will be sent through a tree developed from randomly choosing nine of the sets. The misclassification for this set will be calculated, and performed 10 times until each set has been sent through a tree. An average rate of misclassification is developed to determine how well the tree based on all the data will perform on new data.

Sample Size Calculation and Feasibility: Based on our 18 month data from the two medical centers, there were a total of 1087 patients who remained on mechanical ventilation for at least 48 hours and lived to be discharged to home or self-care. For recursive partitioning, there are no specific sample size calculations. However, in a simulated data analysis, a sample size of 200 yielded an area under the curve (AUC) of .75 for the resultant tree algorithm. To be conservative, we will enroll a total of 225 patients. Based on our estimated number of ARF survivors, we will need to obtain consent from only 20.6% of them to achieve our enrollment goal. This is a very conservative estimate for obtaining informed consent for research on swallowing function.

Additional Considerations: Our primary analysis will develop a CPR for the combined outcome of silent and non-silent aspiration. We will also develop a CPR for silent aspiration alone defined as a PAS score =8, and a CPR for non-silent aspiration alone defined as a PAS score of 6-7. For each of the five different consistencies, the accuracy of the BSE assessment for aspiration will also be compared to the presence of aspiration of the FEES examination (PAS ≥6). Sensitivity, specificity, positive and negative predicted values will be determined with 95% confidence intervals for each point estimate. Based on a sample size of 225 patients, the width of each 95% confidence interval point estimate will be 2-4%.

Statistical analysis for Aim #2: For each outcome and independent variable, a univariate logistic regression model will be developed. If the Wald test for an individual variable in the logistic regression model is significant at the p <0.10 level, the variable will be included in a multivariable logistic regression model. ROC curves will be constructed to determine how well the regression models correctly predict

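### The 2-4% confidence interval width promised with 225 patients cannot be reproduced; at the protocol's own rates the full widths are about 12 to 28 percentage points

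*Combined protocol and SAP*

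**What the plan says.** Under Statistical analysis for Aim #1, the Additional Considerations paragraph plans an analysis by consistency: "For each of the five different consistencies, the accuracy of the BSE assessment for aspiration will also be compared" with aspiration on FEES (PAS score of 6 or more). Sensitivity, specificity, PPV and NPV are each to carry a 95% confidence interval. The forecast precision is: "Based on a sample size of 225 patients, the width of each 95% confidence interval point estimate will be 2-4" per cent. No formula, assumed accuracy, prevalence or denominator is given, and the text does not say whether width means full width or half-width.

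The other figures that bear on this are:

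- **Aspiration rate.** The Significance section says: "Occurring in as many as 44% of ARF survivors, aspiration is associated with many deleterious consequences". Preliminary Data, item 5, reports from 26 pilot patients: "A total of 50% of ARF survivors had evidence of aspiration on FEES evaluation".
- **Expected accuracy.** The only source is "Table 1: BSE accuracy for aspiration with different consistencies".
- **Consistencies tested.** The bolus protocol states: "In order to limit the complexity and duration of our consistency testing, honey-thick liquids will be excluded from the protocol". That row of Table 1 therefore does not apply to the study.
- **Basis for the sample size.** The 225 comes from a simulation in which "a sample size of 200 yielded an area under the curve (AUC) of .75 for the resultant tree algorithm", not from interval width.

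**The concern.** A 95% interval only 2-4 points wide around a proportion in the middle of the range needs a denominator in the hundreds or thousands. Here each measure uses only part of the 225 patients. The stated width therefore looked too narrow by a large factor.

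This is the only precision statement for the accuracy estimates by consistency, and the study hypothesis is about which consistencies give the most accurate bedside diagnosis. A reader who relies on it would expect estimates sharp enough to separate consistencies a few points apart. The study will not deliver that.

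**Working it through.** **Inputs.** N = 225 and 95% confidence (z = 1.96), from the Aim #1 statistical section. Aspiration rates are 44% (Significance) and 50% (Preliminary Data, item 5). Sensitivity/specificity from Table 1 are: nectar 25/62%, thin 38/75%, puree 13/75%, regular solids 38/63%. Ice chips are the fifth consistency, but Table 1 has no row for them.

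**Formulas.** Full width = 2 × 1.96 × √(p(1−p)/n); half-width is half of that. The denominators n are:

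- sensitivity: aspirators, D = 225 × rate = 99 or 112.5
- specificity: non-aspirators, H = 225 − D = 126 or 112.5
- PPV: test-positives, T = D × sens + H × (1 − spec)
- NPV: test-negatives, 225 − T

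PPV and NPV are those implied by the assumed rate, D × sens / T and H × spec / (225 − T).

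**Attempt to reproduce 2-4%.** The most favourable denominator for a single consistency puts all 225 patients behind every measure. At p = 0.13 the half-width is 1.96 × √(0.13 × 0.87/225) = 4.4 points; at p = 0.50 it is 6.5 points. All other Table 1 values fall between these. Full widths are 8.8-13.1 points. Solving the formula for p at n = 225, a 4-point half-width needs a true value of at least 89.5% or at most 10.5%. A 4-point full width needs at least 97.6% or at most 2.4%. No Table 1 value meets either condition.

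**Correct denominators, worked example.** Puree at 50%: T = 112.5 × 0.13 + 112.5 × 0.25 = 42.8 and PPV = 14.6/42.8 = 0.342. The full PPV width is 3.92 × √(0.342 × 0.658/42.8) = 28.4 points.

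**All results (full width, percentage points).**

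| Rate | Consistency | Sensitivity | Specificity | PPV (test-positives) | NPV (test-negatives) |
|---|---|---|---|---|---|
| 44% | Nectar | 17.1 | 17.0 | 21.8 (72.6) | 15.9 (152.4) |
| 44% | Thin | 19.1 | 15.1 | 23.5 (69.1) | 15.3 (155.9) |
| 44% | Puree | 13.2 | 15.1 | 26.7 (44.4) | 14.6 (180.6) |
| 44% | Regular | 19.1 | 16.9 | 21.2 (84.2) | 16.4 (140.8) |
| 50% | Nectar | 16.0 | 17.9 | 22.8 (70.9) | 15.7 (154.1) |
| 50% | Thin | 17.9 | 16.0 | 22.8 (70.9) | 15.7 (154.1) |
| 50% | Puree | 12.4 | 16.0 | 28.4 (42.8) | 14.5 (182.2) |
| 50% | Regular | 17.9 | 17.8 | 21.3 (84.4) | 16.5 (140.6) |

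Half-widths therefore run from 6.2 to 14.2 points. Wilson full widths agree with these within about 1 point. Clopper-Pearson widths are up to about 1.5 points wider.

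**What 2-4% would require.** At n = 99 to 126, a 4-point half-width needs a sensitivity or specificity of at least about 94-96%, or at most about 4-6%. At 90%, the full width is still 3.92 × √(0.09/126) = 10.5 to 3.92 × √(0.09/99) = 11.8 points. At 38% sensitivity, a 4-point half-width needs 0.38 × 0.62 × (1.96/0.04)² ≈ 566 aspirators. A 4-point full width needs 0.38 × 0.62 × (1.96/0.02)² ≈ 2,263.

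**If the reference is aspiration on that single consistency.** The documents give no rate for this, so I assume 20-30%, which gives 45-68 aspirators. At 38% sensitivity the half-width is then about 12-14 points. At 62-75% specificity it is about 6-8 points.

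**The case against.** **Other routes to 2-4%.** Two calculations land in or near the stated range. One standard error at n = 225 is 2.2-3.3 points over the Table 1 values. Pooling boluses as if they were independent gives full widths of 2.6-3.9 points with 225 × 11 trials, or half-widths of 2.0-2.9 points with 225 × 5. Either may be where the figure came from, but this cannot be established. Neither is the 95% interval for each consistency that the text describes, so neither rescues the sentence.

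**Soft inputs.** This objection stands in part. The 44% is an upper figure and the 50% comes from 26 patients. Searching all two-by-two tables of up to 26 patients, each of the four Table 1 rows used here has one solution, with 8 aspirators and 8 non-aspirators (the unused honey-thick row gives 7 and 9). That is an inference, but it shows how uncertain the pilot accuracies are. Both aspiration rates are also per patient, in line with the primary outcome of aspiration "on the FEES with any of the five feedings", while the analysis by consistency does not say which reference it uses. The computed ranges are conditional on these inputs and do not bound every case. The conclusion does not depend on them: the inverted formula shows that only near-extreme accuracies would give 2-4%, and Preliminary Data, item 5, itself describes the accuracy of individual consistencies as apparently poor.

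**Limited consequence.** This is an additional descriptive analysis. Its actual intervals will be reported, and no decision rule uses the forecast width. That limits how serious the error is; it does not make the figure right.

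**Conclusion.** The concern holds. The 2-4% figure is wrong as a full width and as a half-width at every aspiration rate and accuracy that the protocol gives for the consistencies still tested. Against the top of the stated range, the narrowest recomputed interval (puree sensitivity at 50% aspiration, 12.4 points full, 6.2 half) is about 3 times too wide read as a full width and about 1.5 times read as a half-width. The widest (puree PPV at 50%, 28.4 points full) is about 7 times the stated 4 points.

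These sizes assume 44-50% aspiration on any feeding as the reference, the Table 1 accuracies for four consistencies, and all 225 patients contributing to each. Ice chips are not covered. The bolus protocol lets the clinician stop testing early, so some denominators will be smaller and those intervals wider.

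The error misstates the precision of this one analysis and should be fixed. It does not touch the basis for 225 patients or the primary tree analysis.

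**What to change.** Replace the precision sentence in Additional Considerations with wording such as:

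> Assuming that 44-50% of patients aspirate on any feeding (about 99-112 aspirators and 113-126 non-aspirators) and accuracies like those in Table 1, the 95% confidence intervals will be about ±6 to ±10 percentage points for sensitivity, ±8 to ±9 for specificity, ±7 to ±8 for NPV and ±11 to ±14 for PPV. Sensitivity intervals will be wider if the reference is aspiration on that single consistency, and all intervals will be wider where boluses are not given.

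In the same place, state whether the reference is aspiration on any feeding or on the matching consistency, name the interval method, and note that ice chips have no pilot figures.

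The cost is a short edit to the statistical section and a less favourable stated precision. No extra patients are needed, and neither the design nor the primary analysis changes.

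### Aim 2's univariate Wald screen at p<0.10 shuts a completely associated abnormality out of the adjusted model and, when effects are modest, biases upward the odds ratios of those that pass

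*Combined protocol and SAP*

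**What the plan says.** Under Statistical analysis for Aim #2 the combined protocol and SAP states: "For each outcome and independent variable, a univariate logistic regression model will be developed". It continues: "If the Wald test for an individual variable in the logistic regression model is significant at the p <0.10 level", then "the variable will be included in a multivariable logistic regression model". The section goes on to ROC curves, a confounding check that uses baseline demographics, and a power statement for the univariate comparison. None of these readmits a candidate that failed the screen. No likelihood-ratio, exact or penalised method is named, nothing is said about sparse or empty cells, and no shrinkage or other allowance for selection is planned.

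The opening summary gives the Aim 2 outcomes as "Presence of abnormalities in the four laryngeal functions and two swallowing physiology measures", which makes six variables. The Significance section lists them: laryngeal sensory deficit, edema, vocal fold immobility, granuloma, delayed swallow and reduced clearance. Specific Aim #2 puts the question the other way round: "To identify abnormalities in laryngeal structure and swallowing physiology that are associated with aspiration in ARF survivors".

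The sample size is fixed by "To be conservative, we will enroll a total of 225 patients". On the aspiration rate, the Significance section says "Occurring in as many as 44% of ARF survivors"; the protocol's own 26 pilot patients had 50%. Item 6 of the Preliminary Data reports: "Vocal cord granulomas were associated with severe dysphagia or aspiration" (p = 0.04, from 59 patients), just after describing upper airway abnormalities, granuloma included, as common.

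**The concern.** Two properties of this rule work against an aim that exists to find abnormalities associated with aspiration.

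First, the Wald statistic is unreliable exactly where an association is complete. If every patient with a lesion aspirates, the log odds ratio has no finite maximum. Its standard error grows faster than the estimate, so the p-value approaches 1 and the variable fails the entry test because its association is too strong.

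Second, when the same data decide which variables enter and also estimate their effects, a weak effect passes mostly when chance has exaggerated it. The adjusted odds ratios and intervals then carry no sign of that selection.

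The adjusted Aim 2 results, which are meant to point to targets for treatment, could omit a complete association or overstate a modest one. With only six pre-named candidates, little is gained by screening.

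**Working it through.** **Inputs.** From the documents: N = 225; aspiration 44%, so 0.44 × 225 = 99 aspirators, or 50%, so about 112; entry at Wald p < 0.10 (taken as two-sided, |z| > 1.645, since sidedness is not stated). Assumed, because the documents give none: abnormality prevalences, true effects above the planned range, and correlations among the abnormalities.

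**The plan's own figure.** The section's only figure is 178 to 271 observations for 80% power at odds ratios of 2.5 to 3.0. It cannot be reproduced without a prevalence. At 44% aspiration, an odds ratio of 2.5 needs 236, 201 or 180 patients at 20%, 25% or 30% prevalence, so the range is plausible. It is not disputed here.

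**Step 1: the empty cell.** Take 8 carriers, all aspirating, and 217 non-carriers, 91 aspirating and 126 not.
- Wald: log OR = ln[(8 × 126)/(0 × 91)] is infinite, and SE = √(1/8 + 1/0 + 1/91 + 1/126) is infinite. Software stops at an arbitrary large value. After 20 iterations I get 21.5 with SE 8,619, p = 0.998.
- Likelihood ratio: the null log-likelihood is 99 ln(99/225) + 126 ln(126/225) = −154.33. The fitted one is 91 ln(91/217) + 126 ln(126/217) = −147.58. Twice the difference is 13.5, p = 0.0002.
- Fisher: (99/225)(98/224)…(92/218) = 0.0012. The two-sided p is the same, because the opposite extreme (0 of 8) is more probable.

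With 5 of 5 carriers, the likelihood-ratio p is 0.004, Fisher's p is 0.016 and the Wald p is again about 1. A near-miss also fails. With 4 of 5, log OR = ln[(4 × 125)/(1 × 95)] = 1.66 and SE = √(1/4 + 1 + 1/95 + 1/125) = 1.13, so z = 1.47 and p = 0.14. A 2×2 odds ratio is symmetric, so the failure occurs whichever side of the regression aspiration is on.

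**Step 2: how often a cell is empty.** With prevalence B and carrier risk p₁ (set so that 44% aspirate overall), the chance that there is at least one carrier and all carriers aspirate is (1 − B + B p₁)^225 − (1 − B)^225. For B = 5% and OR 6, p₁ = 0.813, giving 0.121.

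| Prevalence | OR 2.5 | OR 3.0 | OR 6 | OR 10 |
|---|---|---|---|---|
| 5% | 1.9% | 3.0% | 12% | 25% |
| 10% | 0.03% | 0.07% | 1.1% | 4.8% |
| 20% | ~0 | ~0 | 0.002% | 0.06% |

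**Step 3: bias after selection.** I simulated 225 patients with six binary abnormalities and 44% aspiration, applied the screen, then fitted the survivors jointly (8,000 runs per setting, geometric mean odds ratios, runs with a diverging estimate left out).
- True OR 1.5 for all six, the variable of interest at 10% prevalence and the others at 20% to 50%. With latent correlation 0.3 it passes in 54% of runs and is then reported at about 2.2. With independence it passes in about 23% and is reported at about 2.7. Entering all six without a screen gives about 1.5 in both cases.
- True OR 2.5 for all six at 20% prevalence. With correlation 0.3: 2.66 screened against 2.63 unscreened, 2.66/2.63 = 1.01. With independence: 2.92 against 2.60, 2.92/2.60 = 1.12.

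**Step 4: can the full model be supported?** 99/6 = 16.5 and 112/6 = 18.7 aspirators per term, if each abnormality is one term.

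**The case against.** The strongest reply is that the empty cell is an edge case. The only prevalence information in the protocol is that these abnormalities are common, and at 10% prevalence or more an empty cell is unlikely even for large effects. At the planned odds ratios of 2.5 to 3.0 it is rare even at 5%. This stands, and it limits how much weight the first problem can bear.

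Several stronger readings are tempting, and the documents do not support them:
- A reader might infer that granuloma is about to be screened out. The pilot association was with a combined outcome of severe dysphagia or aspiration. Nothing suggests that granuloma is rare or that every patient with one aspirates.
- A reader might infer that a complete association would vanish from the report. A univariate model is fitted for every variable, and nothing says its result is suppressed. What is lost is the adjusted estimate.
- A reader might infer that all reported odds ratios will be too large. The bias is an average and depends on effect size and prevalence. It is small at the planned effects once prevalence reaches about 20%.
- A reader might infer that the screen will also hide abnormalities masked by one another. That needs negative correlations. The documents report none, and the Background attributes the abnormalities to shared causes such as the endotracheal tube and deconditioning.

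It can also be objected that the opening summary makes the abnormalities the outcomes, so that a six-term model for aspiration is not what was planned. The text does conflict with itself here. The wording of Specific Aim #2 favours aspiration as the response, but the plan has to say so.

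Finally, the FEES scoring form grades several laryngeal items, records mobility and sensation by side, and records onset time and clearance for each bolus. Six terms are therefore not automatic. This stands, and the fix has to include a coding rule.

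**Conclusion.** The concern holds in a limited form. That the rule fails on an empty cell is arithmetic and does not depend on assumptions. How often this would happen does: 12% to 25% of trials at 5% prevalence with a true odds ratio of 6 to 10, 1% to 5% at 10% prevalence, and under 0.1% at 20%. The upward bias is material for modest effects in uncommon abnormalities (true 1.5 reported at about 2.2 to 2.7 at 10% prevalence) and about 1% to 12% at an odds ratio of 2.5 and 20% prevalence. The prevalences and correlations behind these figures are assumed. Severity is minor to moderate and confined to the adjusted results of Aim 2; the Aim 1 prediction rule is unaffected.

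**What to change.** 1. Reconcile the opening summary's list of Aim 2 outcomes with Specific Aim #2, and state which side of the regression aspiration is on.
2. With aspiration as the response, remove the p<0.10 screen and enter the six pre-named abnormalities together. State in advance how each is reduced to a single term: grades, sides and repeated bolus trials.
3. Use Firth's penalised likelihood with likelihood-ratio or profile-likelihood tests and intervals, so that an empty cell gives a finite estimate. In a 2×2 table this amounts to adding 0.5 to each cell, so the 8-of-8 example gives (8.5 × 126.5)/(0.5 × 91.5) = 23.5.
4. If a screen is kept, base it on the likelihood-ratio test. For an abnormality of 2% to 8% prevalence whose carriers always aspirate, such a screen retains it in 94% to 100% of simulated trials, against none with the Wald screen. It does not remove the selection bias, so the adjusted odds ratios should be reported as subject to selection.

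The cost is a short change to the analysis text plus the coding rule, with standard software and no extra patients or data. The downside is slightly wider intervals from carrying weak terms.
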